Rationale for the study design: Pilot work with HOPE has determined that HOPE is associated with improved outcomes relative to standard shelter services alone. Given that there is no other existing PTSD treatment appropriate for this population that could serve as a comparison condition the next logical stage in evaluating the efficacy of HOPE is to determine if HOPE offers improvement over a credible control condition that controls for the nonspecific components of therapy. PCT (see appendix) is a problem-focused, supportive therapy that is frequently used as an attention-matched control condition in clinical trials of PTSD^{46, 47}. PCT does not incorporate any of the hypothesized active ingredients of HOPE (e.g., cognitive-restructuring, acquisition of new behavioral skills, safety planning, access to resources, and empowerment strategies), but does provide psychoeducation on PTSD. Further, PCT is also clinically realistic, as many practitioners incorporate this approach into their standard practice⁴⁸. Therefore, we chose to compare HOPE to PCT, in order to determine if components specific to HOPE are responsible for observed effects, rather than nonspecific factors consistent with supportive therapy. [name] who has established expertise in PCT⁴⁶ will assist in adapting PCT to meet the needs of the proposed study, as well as in the training and supervision procedures for the PCT arm of this study.

Sample and recruitment: Participants will be 186 women recruited over 27 months from six battered women's shelters in five different counties within a 55 mile radius of the University of Akron (see letters of support) and randomized either to receive HOPE ($n = 93$) or PCT ($n = 93$). Both treatments will start while women are residents of shelter and extend after they leave shelter. Given that the length of shelter stay is variable and outside of experimenter control, session frequency will be individualized based on length of shelter stay. We are currently employing this model in our work with HOPE with success (see C1). Participants in both treatment conditions will receive up to ten individual sessions while in shelter, and 16 sessions in for up

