Randomization: In order to ensure that the treatment conditions are balanced on variables that might influence outcome (i.e., use of psychotropic medications and substance use), participants in each subgroup will be assigned to their treatment condition using an urn randomization procedure⁵⁴. Urn randomization is a stratified randomization technique that randomly assigns participants in a given subgroup to treatment conditions, but systematically biases the randomization in favor of balance among treatment conditions. We will stratify participants according to comorbid substance use disorder (SUD) and use of psychotropic medications to obtain an equal distribution of participants using medications or with SUD in each condition.

Potential for Cross-Contamination: The shelter is a close community and participants in HOPE may share HOPE specific components with participants in PCT. We considered randomizing treatment assignment to shelter rather than participants in an effort to eliminate the potential for cross-contamination. However, this strategy significantly reduced our power and required a sample size that was not feasible or cost effective. Further, in our pilot work with HOPE only 2 participants in the control group reported that participants in HOPE shared HOPE-specific information with them, with exploratory analyses revealing no differences in PTSD outcomes between those who reported exposure and those who did not. Further, HOPE focuses on empowerment and provides individualized feedback and customized handouts, thus the content of HOPE cannot be easily learned through exposure to a handout or a brief conversation. However, to minimize the likelihood of cross-contamination between treatment and control groups, we will (1) instruct participants to not share their materials (i.e., workbook) with other shelter residents, (2) assess whether participants randomized to HOPE shared HOPE specific information with other shelter residents, and whether participants randomized to PCT were exposed to specific HOPE components during our follow-up procedures, and (3) assess use of HOPE specific skills in the PCT group in order to determine if women in PCT were actually implementing skills taught only in HOPE. Thus, we will try to minimize the potential for sharing HOPE-specific information and skills between participants, but also assess whether cross-contamination is a significant problem (see C3).

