Noncompleters: In general, women who do not attend at least 8 sessions (i.e., $\frac{1}{2}$ of sessions, as prior work with HOPE finds treatment effects when participants attend approximately 50% of sessions) will be considered noncompleters. Women will not be discontinued from the treatment protocol for noncompliance. All women will be invited to continue treatment and follow-up assessments. Given the unpredictable and demanding lives of our target group, most of whom are low-income, flexibility is important to make the treatment accessible to them (see assessment and retention sections for how we will address barriers in scheduling appointments).

Clinical Deterioration/Suicidal Risk. To increase safety, participants will be removed from the treatment phase of the trial as a result of clinical deterioration or suicidal risk (see E1 for procedures, assessment & definitions). Participants will remain in the research sample, be followed, and included in all analyses.

Therapists: Therapists for the intervention will consist of 4 community therapists who have been rated as qualified practitioners of HOPE or PCT (see below). Licensed, Master level (psychology, social work, counseling, or other related field) therapists will be recruited from the two local community mental health agencies who have served as our primary referral sources for this population throughout our pilot work (and thus are representative of the types of agencies most likely to treat victims of IPV who seek shelter). Each therapist will be required to have a minimum of two years of experience working with trauma populations, as well as training and experience in CBT interventions. Potential therapists will be interviewed by the PI. The interview will include questions about their training in trauma and CBT. Role-plays will also be used to assess the adequacy of their training and their ability to learn the proposed treatment protocols.

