Therapist training procedures: Procedures for training and monitoring therapists will mirror those used in prior research utilizing community therapists⁵⁵. [name], will assist in refining the training and monitoring protocols of community level therapists. To optimize the rapid acquisition and maintenance of therapist skills, supervision will initially be intensive, with supervision being titrated to skill level so that it becomes less intensive as therapists acquire more experience. [name] will oversee weekly group supervision sessions with all community therapists. [name] will provide individual supervision titrated to skill level to each of the community therapists. [name] and the project coordinator will review therapists' audiotapes on a weekly basis and provide feedback during individual and group supervision sessions. The therapists will be closely monitored for competence and adherence throughout the study and if at any time a therapist does not achieve good adherence, the therapist will be replaced with another therapist who will have received the training and completed the certification process. If a therapist has problems delivering the treatment, then data associated

with this therapist will not be included in any analyses. We are confident that we will be able to successfully train community therapists in HOPE, as we have successfully trained master-level graduate students in HOPE in our prior research. Further, we are using rigorous training procedures that have been successful in prior clinical trials with PTSD treatments⁵⁵. Finally, HOPE is a very structured treatment with a detailed and well scripted manual, leaving very little room for therapists to veer from standardized treatment procedures.

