The four community therapists will be trained in either the conduct of HOPE or PCT. We chose to train therapists in only one treatment modality in order to eliminate the risk of contamination in the control group and assure that HOPE is compared to a true attention-matched control condition. Therapists will be randomly assigned to deliver either HOPE or PCT. Existing systematic training programs (certification processes) in the conduct of HOPE and PCT that have been implemented in prior research will be used for the proposed study. As in prior research utilizing community therapists⁵⁵ each therapist will have two closely supervised training cases prior to taking on participants enrolled in the randomized trial. For both HOPE and PCT, the overall training objectives are for therapists to understand and learn to perform the intervention, to avoid using techniques or materials not part of the intervention, to ensure the use of relatively consistent procedures across different participants, and to deliver the intervention in a culturally sensitive manner. HOPE training (see training manual in appendix) includes a two-day workshop on HOPE conducted by [name], that includes lectures on IPV and PTSD, the theoretical conceptualization of HOPE, and the structure of, techniques used in, and conduct of HOPE sessions. The training program will also teach strategies for maintaining the therapist and participant safety when conducting HOPE sessions post-shelter, as well as procedures for managing emergency situations. Role-plays of appropriate and effective as well as faulty strategies to conduct the sessions, and strategies to manage participants whom may have difficulty in comprehending or utilizing the techniques will be included in the workshop. PCT training will also include a two-day workshop on PCT conducted by [name]. Drs. [name] and [name] will work closely with [name] in adapting the existing didactic training program for this study. Therapists will be trained in general issues in working with IPV victims, including strategies for managing emergencies. The workshop will include a description of the theoretical rationale behind PCT, as well as specific PCT strategies. Training will also be provided outlining specific strategies that are not to be used as a part of PCT (e.g., cognitive-restructuring, skills training, and other overlapping components with HOPE). Role-plays of appropriate and effective as well as faulty strategies to conduct the sessions, and strategies to manage more difficult clients will be included in the workshop.

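### As worded, weekly group supervision with tape feedback includes therapists from both arms, leaving open a therapist-level route for HOPE content to reach PCT that single-modality training was meant to close.

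*Combined protocol and SAP*

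**What the plan says.** All references are to the combined protocol and SAP.

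- **Who the therapists are** (C2, Therapists): "4 community therapists who have been rated as qualified practitioners of HOPE or PCT". Whichever arm they deliver, they must have "training and experience in CBT interventions".
- **How they are supervised** (C2, Therapist training procedures): a supervisor "will oversee weekly group supervision sessions with all community therapists". A supervisor and the project coordinator also "review therapists' audiotapes on a weekly basis and provide feedback during individual and group supervision sessions". Intensity is to fall as therapists gain skill.
- **Why each therapist learns one treatment** (same section): "We chose to train therapists in only one treatment modality in order to eliminate the risk of contamination in the control group".
- **What the control is meant to be** (C2, Rationale for the study design): "PCT does not incorporate any of the hypothesized active ingredients of HOPE". The same section says a PCT expert will assist with training and supervision procedures for the PCT arm.
- **Contamination checks** (C2, Potential for Cross-Contamination): the section is framed around residents sharing material. It includes asking "whether participants randomized to PCT were exposed to specific HOPE components during our follow-up procedures" and assessing whether PCT women use HOPE skills.

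**The concern.** The plan accepts the cost of therapists who each deliver only one treatment in order to keep the control clean. It then appears to bring those therapists together every week to discuss cases with feedback from tapes. PCT therapists are told not to use cognitive restructuring or skills training, yet their required background means they already hold some of these skills. The protocol's reassurance that HOPE is hard to pick up casually concerns residents and brief exposure, not licensed clinicians in regular supervision.

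Any uptake of HOPE techniques in PCT would shrink the HOPE-PCT difference on both primary outcomes, PTSD severity and re-abuse severity. It would also weaken the inference PCT was chosen to support, namely that any benefit comes from components specific to HOPE.

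**Working it through.** **1. The text side by side.** The point rests on wording, not arithmetic.

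- The Therapists paragraph makes the four community therapists a mixed group, HOPE or PCT.
- The supervision sentence applies to all of them, weekly, and tape feedback is given in group as well as individually.
- No section splits the group by arm or limits tape feedback to the therapist's own modality. The nearest hint is the PCT expert's help with PCT-arm supervision procedures, which does not say that groups are separate.

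**2. What each safeguard does to this route.**

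| Safeguard | Where | Effect |
|---|---|---|
| Training on strategies barred from PCT; objective of avoiding techniques from outside the intervention | C2, Therapist training procedures | Discourages drift |
| Weekly tape review, adherence monitoring, therapist replacement | C2, Therapist training procedures | Detects drift, acts afterwards; some feedback returns to the group |
| Rating of 5% of sessions (74 per arm) by a HOPE-trained rater | C2, Adherence and Competence | Can detect drift in a sample |
| Participant reports of HOPE exposure and skill use | C2, Potential for Cross-Contamination; Satisfaction with Treatment | Can detect drift whatever its source |
| Exposed versus unexposed controls; preliminary therapist effects | C3, opening paragraph | Explores impact afterwards |
| Dropping a therapist's data, or cases with inadequate adherence | C2, Therapist training procedures; C3, Treatment Integrity | Removes data after the fact |

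None of them keeps PCT therapists out of HOPE case discussion. With four therapists over two arms, excluding one could remove a large share of an arm.

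**3. The plan's own power figure.** Inputs from C2, Adequacy of Sample Size: J = 6 shelters, n = 25 analysed per shelter, effect size δ = .60, effect-size variance .07, variance explained by shelter B = .1, variance explained by baseline R² = .3, α = .05. Sidedness is not stated; the F test used here is two-sided.

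For a multisite trial with random site effects, the test is F with (1, J − 1) = (1, 5) degrees of freedom and noncentrality

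λ = J·δ² / [variance + 4(1 − B)(1 − R²)/n]

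- Denominator: .07 + 4 × .9 × .7 / 25 = .07 + .1008 = .1708
- λ at δ = .60: 6 × .36 / .1708 = 12.65
- Critical F(1, 5) at .05 is 6.61, which gives power .809

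The smallest n per shelter reaching .80 is 25, so the stated 150 is reproduced.

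**4. Illustration of dilution.** The documents give no contamination rate, so the uptake fractions below are assumptions. With 150 analysed:

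| Assumed PCT uptake of the effect | δ | λ | Power |
|---|---|---|---|
| 0% | .60 | 12.65 | .81 |
| 10% | .54 | 10.24 | .73 |
| 20% | .48 | 8.09 | .63 |
| 30% | .42 | 6.20 | .52 |

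On the plan's own inputs there is almost no slack: power already starts at about .81.

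**The case against.** The strongest reply is that a joint meeting is inferred. The protocol speaks of sessions in the plural and of someone overseeing them, and it mentions supervision procedures for the PCT arm. Separate groups are therefore not strictly excluded, and what the group discusses is not described. This stands as a limit on certainty. Joint attendance is still the plainer reading, and no sentence states separation.

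The second reply is that drift is watched for. Tapes are reviewed weekly, a therapist who does not achieve good adherence is replaced, a HOPE-trained rater scores PCT sessions, and the questions on exposure and skill use would register HOPE content delivered by a PCT therapist as well as by a fellow resident. This also stands: drift need not go unseen. These measures act on drift once it is under way, however, and do not close the route.

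A reader might go further and infer the following. The documents support none of it.

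- **That all 93 PCT women are exposed and the C3 contamination comparison has no clean reference group.** Attending a meeting is not delivering HOPE. Drift could differ by therapist, case and time, and exposure is recorded for each woman. The reference group would be lost only if drift were uniform.
- **That there would be about 130 joint sessions.** Recruitment of 27 months plus 3 months of post-shelter treatment gives 30 × 52/12 = 130 weeks. This is an upper bound, because it assumes joint and undiminished weekly meetings while supervision is planned to taper.
- **That HOPE would be blurred in turn.** The protocol describes HOPE as closely scripted, and nothing shows flow in that direction.

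**Conclusion.** The concern holds as a gap in the design as worded. Group supervision with tape feedback is not separated by arm, which is at odds with the reason given for single-modality training. What is established is an open route at therapist level, not contamination itself. Its occurrence and size cannot be derived from the documents.

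If drift occurred, it would bias HOPE versus PCT toward no difference. The power figures in the illustration are conditional on assumed uptake and on the plan's own sample-size inputs; they do not predict what this design would produce. If separate groups were always intended, a sentence saying so would resolve the main point. The change is worth making because prevention is cheap and the existing remedies work by discarding data.

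**What to change.** In C2, Therapist training procedures:

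1. State that weekly group supervision and tape feedback are held separately for HOPE and PCT therapists, with equal supervision time in the two arms.
2. Have the existing supervisor or supervisors run both groups, with the PCT expert assisting as C2, Rationale for the study design, already plans. Asking that expert to lead a weekly group would go beyond the assisting role described.
3. Limit any joint meeting to logistics and emergencies, with no session content.

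In the tape review (same section) and in C2, Adherence and Competence, have the existing review and the planned ratings of PCT sessions record any HOPE-specific content.

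The cost is protocol wording, one extra or split supervision slot a week, and an added item in the tape review and ratings. No new staff are needed if the existing supervision runs both groups. The downside is small peer groups, about two therapists each if the four are divided evenly, a split the protocol does not state.

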LIFE	X		X	X		X		X		X
CSQ						X		X		X

Note. MSSSI administered at any time point if participant endorses SI. CAPS administered at mid-tx assessments if DTS increases 50%. *Only the substance module of SCID-I/P administered at follow-up.

Adherence and Competence: All therapy sessions will be recorded. [name], a consultant on this project who is well-trained in treatment of IPV-related PTSD, as well as in HOPE, serving as a therapist in our pilot work with HOPE will rate adherence and competence of the delivery of 5% of randomly selected HOPE and PCT sessions (i.e., 74 HOPE and 74 PCT sessions). She will also participate in the PCT training with the study therapists and consult with [name] in order to develop competence in rating PCT sessions. HOPE and PCT have established adherence and competence scales used in prior research (see appendix)^{37, 46}.

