Prior to conducting analyses for the main project aims, a series of routine procedures will be conducted to ensure the data accuracy/adequacy. We will also examine the distribution of our key variables for skewness, variability, missing data, and outliers. Data will be transformed to achieve normality if needed. At this time, we will also assess the effectiveness of the randomization procedures. If between-group differences exist, relevant variables will be included as covariates in outcome analyses. We will also explore whether contamination is a significant issue by comparing members of the control groups reporting they were exposed to specific HOPE content to those who were not exposed to determine if such exposure impacts outcome, and control for exposure in analyses below if necessary. Although only a small percentage of participants in our pilot work reported initiation of a new medication (3.3%), change in dose or type of ongoing medications (3.3%), or cessation of a medication (5%), we will also explore whether medication changes during treatment impacted outcome, and control for medication changes in analyses if necessary (see below). Additionally, we will preliminarily investigate therapist effects on attendance, attrition, and primary outcomes and use this data to inform future research with HOPE that will more directly assess therapist effects. Finally, pattern mixture methods^{74, 75} will be used to assess the ignorability of missingness in all outcome analyses described below. All analyses will include an intent-to-treat analysis (using data from all randomized participants) and a minimal attendance analysis (i.e., attending at least $\frac{1}{2}$ of sessions). For intent-to-treat analyses, missing data will be handled using multiple imputation with an expectation maximization algorithm.

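### If any therapist is judged to have delivery problems, the plan both deletes that therapist's participants from every analysis and requires an intent-to-treat analysis of everyone randomized

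*Combined protocol and SAP*

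**What the plan says.** Two sections define who is analysed.

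- **C2, Therapist training procedures.** "If a therapist has problems delivering the treatment, then data associated" "with this therapist will not be included in any analyses" (one sentence, split by a page break). The sentence before it covers monitoring over the whole trial and replacement of a therapist whose adherence is not good.
- **C3, Data Analytic Plan.** "All analyses will include an intent-to-treat analysis (using data from all randomized participants"), "and a minimal attendance analysis", the latter defined by attending at least half the sessions. Missing data in the intent-to-treat analysis are to be multiply imputed.

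Three other places bear on the point.

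- **C2, Clinical Deterioration/Suicidal Risk**, on women taken out of treatment for safety: "Participants will remain in the research sample, be followed, and included in all analyses".
- **C2, on therapist assignment:** "We chose to train therapists in only one treatment modality in order to eliminate the risk of contamination in the control group". Each therapist therefore works in one arm.
- **C3, Treatment Integrity** also drops cases with an inadequately delivered session, without saying from which analyses.

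**The concern.** A woman treated by a therapist who is later judged to have delivery problems cannot be both left out of every analysis and counted among all those randomized. An analyst following the text could produce either of two datasets for PTSD severity and re-abuse severity and claim compliance with the plan.

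The literal C2 rule has three features that make it harmful:

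- The trigger is a post-randomization event, so deleting on it forfeits the protection of randomization.
- The supplied text gives no cut-off or timing for what counts as a problem. C2 (Adherence and Competence) says "HOPE and PCT have established adherence and competence scales used in prior research", but those scales are in an appendix that was not supplied. It is also unclear whether the trigger is the same as the poor-adherence trigger for replacement.
- Each deletion falls on one arm. The staff who review session tapes will know which treatment they are hearing, so the decision cannot be blind to arm.

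If more difficult cases lead to poorer delivery, the deleted women would differ systematically from those kept. Whether this happens, and in which direction it would push the result, depends on how women are allocated to therapists within an arm. The documents do not state that.

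**Working it through.** **Step 1. Can the two sentences be read together?**

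- *The C2 exclusion covers only pre-trial training cases.* This fails. The adjoining text is about monitoring for the whole trial, and training cases are a separate, earlier step: "each therapist will have two closely supervised training cases prior to taking on participants enrolled in the randomized trial".
- *It covers only the minimal attendance analysis.* This fails. C2 says any analyses, and C3 defines that analysis by attendance, not by therapist.
- *The data are set to missing and imputed.* The plan does not say this, and it would discard observed outcomes.
- *C3 governs because it is the analysis section.* No supplied text says so, and C3 (Treatment Integrity) itself contains a delivery-based exclusion of unstated scope.

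No reading removes the conflict once a therapist triggers the rule. If no therapist does, both sentences can be followed.

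**Step 2. Reproduce the plan's sample size.** Inputs from C2 (Adequacy of Sample Size): effect size .60, effect-size variance .07, 6 shelters, .1 of variance explained by shelter, .3 by the baseline covariate, alpha .05, power .80. The sidedness of alpha is not stated, so I used the F test, which is equivalent to a two-sided test.

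For a multisite trial with random shelter effects, referred to a noncentral F(1, J − 1):

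λ = Σ over shelters of .60² / [.07 + .63 × (1/n₁ + 1/n₂)], where .63 = (1 − .1)(1 − .3).

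With 25 analysed per shelter, n₁ = n₂ = 12.5:

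λ = 6 × .36 / (.07 + .63 × .16) = 6 × .36 / .1708 = 12.65, power .809.

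The smallest n reaching .80 is 25 per shelter, or 150 in total, as the plan states. For attrition, 150/.8 = 187.5, close to the planned 186.

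**Step 3. Delete HOPE women.** Let k be the number of randomized HOPE women deleted out of 93 (93/6 = 15.5 per shelter). The analysed fraction is 150/186, assumed equal in both arms and all shelters. The PCT arm stays at n₂ = 12.5 per shelter. With even spread, n₁ = (93 − k) × (150/186)/6. A shelter that loses 10 of its 15.5 HOPE women has n₁ = 5.5 × 150/186 = 4.44.

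| k | Where deleted | n₁ | λ | Power |
|---|---|---|---|---|
| 0 | – | 12.5 | 12.65 | .809 |
| 10 | evenly, 6 shelters | 11.16 | 12.21 | .796 |
| 10 | all in one shelter | 4.44 there, 12.5 elsewhere | 11.91 | .786 |
| 20 | evenly, 6 shelters | 9.81 | 11.70 | .779 |
| 20 | all in two shelters | 4.44 there, 12.5 elsewhere | 11.17 | .761 |
| 46.5 | evenly, 6 shelters | 6.25 | 9.76 | .706 |
| 46.5 | every HOPE woman in three shelters (J = 3) | 12.5 in the other three | 6.32 | .302 |

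The 46.5 rows assume the four therapists split two per arm with equal caseloads (93/2 = 46.5, or 25% of 186). The documents state neither. The last row also assumes that the therapist served three shelters exclusively. C2 (Feasibility) says only that two therapists coordinated with four sites in earlier work, so treat that row as an unsupported extreme.

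**The case against.** The conflict is conditional, and the plan makes the condition less likely: certification, two supervised training cases, weekly tape review, therapist replacement and a scripted manual. Weekly review would normally cut a caseload short, so losing half an arm is improbable, and the .30 figure more so. For 10 to 20 deletions the power loss is small. The explicit intent-to-treat definition sits in the analysis section, while the exclusion is one sentence in a training section, so a sensible reader might let C3 govern and treat the repair as editorial. The rule for women removed for safety concerns a participant-level event, so it is a contrast with the therapist rule and not a second contradiction.

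Most of this stands as a limit on likelihood and size. It does not settle which rule applies. The plan foresees therapist failure, since it provides for replacement. No supplied text gives C3 precedence, and C3's own Treatment Integrity paragraph leaves room for delivery-based exclusions. The safety rule shows that the authors state retention explicitly when they intend it. Limiting the C2 sentence to analyses other than intent-to-treat would also remove the contradiction and gives the same intent-to-treat set as deleting it.

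**Conclusion.** The concern holds. As written, C2 and C3 give different analysis sets for both primary outcomes whenever a therapist is found to have delivery problems. The C2 version is not an intent-to-treat set. This must be fixed, because a choice made after outcomes are seen would not be credible.

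The conclusion rests on the text and on no number. The direction and size of bias are unknown, and the documents do not say how many women would be affected. The power figures are illustrations under the assumptions stated above. They show that power is secondary to the question of who is analysed. The Treatment Integrity exclusion needs its scope clarified but does not add to the seriousness of this point.

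**What to change.** Delete the exclusion sentence in C2 (Therapist training procedures) and add to C3 wording such as:

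> In the intent-to-treat analysis, all randomized women are analysed in their assigned arm regardless of therapist, adherence or competence rating, or attendance. Data from participants of a replaced therapist are retained. The minimal attendance analysis is as defined in this section. Analyses that exclude inadequately delivered cases are supportive sensitivity analyses only.

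In C3 (Treatment Integrity), state that the exclusion of inadequately delivered cases applies only to the treatment-integrity or sensitivity analyses.

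The cost is wording only. Sample size (186) and therapist replacement are unchanged. The trade-off is that the intent-to-treat estimate will include poorly delivered cases and may differ from the effect of well-delivered treatment. The sensitivity analysis would show that difference.
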